3.7 Interim analysis

An interim analysis may be conducted by the Sponsor's decision after receipt of efficacy data for Angal S and ANTI-ANGIN® FORMULA, spray, after 3 days of therapy, on Day 4, for at least 100 patients in every arm. The interim analysis includes demographic data, data of anamnesis and concomitant therapy, available data on efficacy and safety of Angal S and ANTI-ANGIN® FORMULA spray.

Safety will be evaluated for all the patients who received at least one dose of the study drug as at the interim analysis date. Based on the interim analysis results, the main and additional statistical parameters of efficacy and safety of the study drug, ZAO Sandoz shall be entitled to decide to discontinue the trial prematurely.

No significance level correction for the interim statistical analysis is envisaged.

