4.5 Expected duration of the subjects' participation in the trial

Screening period: 1 day.

Treatment period: up to 5 days (including the screening/randomization day).

Follow-up period: up to 2 days.

A maximum duration of each subject's participation: 7 days.

A minimum duration of each subject's participation: 6 days (depending on the arm).

4.6 Description of rules for termination of the trial parts or the trial as a whole

The trial may be terminated on the following grounds:

- 1. Upon the Sponsor's initiative: availability of new toxicological or pharmacological data, or data on SAE which require re-consideration of the previous evaluation of the benefit/risk ratio.
- 2. Upon the Sponsor's initiative: AEs incidence or severity require the trial termination;
- 3. Upon the Sponsor's initiative: other reasons including administrative ones.
- 4. Upon the decision of the regulatory authorities.

The trial may be terminated at a specific trial site in case the patients enrollment or data quality are unsatisfactory, or it is reasonable to assume a breach of GCP and/or Declaration of Helsinki, or other serious protocol deviations.

In case of early termination of the trial, the Sponsor must inform the trial site personnel as well as regulatory authorities with indication of the reason thereof.

The rules for trial termination for every participant are described in Section 5.3.

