9.3 Applicable significance level

All statistical analyses in this trial will be conducted at 95% significance level (a threshold p value for confirmation of statistical significance is below 0.05), except for the primary endpoint where an onesided statistical criterion will be used with 97.5% significance level (a threshold p value is below 0.025). The two-sided statistical criteria will be used for all other parameters.

For the primary endpoint evaluation, 90% CI will be calculated for the proportions difference with further evaluation of its lower boundary limit.

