9.4 Trial termination criteria

The trial may be terminated under conditions described in Section 4.6 of this protocol.

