9.8. Interim analysis

An interim analysis may be conducted by the Sponsor's decision after receipt of efficacy data for Angal and ANTI-ANGIN® FORMULA after 3 days of therapy, on Day 4, for at least 100 patients in every arm. The interim analysis includes demographic data, data on the anamnesis and concomitant therapy, available data on efficacy and safety of Angal and ANTI-ANGIN® FORMULA drugs.

10 Direct access to primary data/documents

Primary data represent entire information contained in original records and certified copies regarding clinical data, observations, and other measures within the trial scope and which is required for reconstruction and evaluation of the trial. The investigator must cooperate for the purposes of monitoring, audit(s), expert evaluation by the Ethics Council and regulatory authorities and provide the access to the primary data/records.

The primary data must be stored in a proper quality throughout the time stipulated for by the local and international laws, as well as written contracts with the Sponsor company. For each subject included, the Investigator must note in the primary records the fact of such participation as well as the following data: an individual identification code, personal data (full name, address), dates of the drug intake, vital signs, any AEs, trial completion dates, the main reasons for discontinuation (if applicable).

The Investigator is obliged to provide direct access to the primary data and documents for the clinical trial specialists and/or authorized representatives (CRO) of the Sponsor, competent bodies' auditors, representatives of the insurance companies, Ethics Committees.

11 Quality control and assurance

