This trial has been designed and conducted to evaluate non-inferiority of the therapeutic efficacy and safety of the study drug Angal S, topical spray [menthol] containing 0.5 mg of lidocaine hydrochloride and 2 mg of chlorhexidine digluconate per ml (Sandoz d.d., Slovenia), when compared to ANTI-ANGIN® FORMULA, topical metered spray giving 0.12 mg of tetracaine hydrochloride and 0.24 mg of chlorhexidine bigluconate per dose (OOO Valeant, Russia) in the treatment of patients with uncomplicated acute infectious and inflammatory diseases of the pharynx accompanied by a sore throat. The objective of this Phase III trial is to demonstrate the non-inferior therapeutic efficacy of the study drug as compared to the reference product.

This Statistical Analysis Plan was developed in accordance with the following documents:

- Guidelines for examination of medicinal products, Vol. 1. Federal State Budgetary Institution Scientific Center for Expert Evaluation of Medicinal Products under the Ministry of Health of the Russian Federation (eds. A.N. Mironov). Moscow: Grif and K, 2013.
- ICH harmonized tripartite guideline. Statistical principles for clinical trials (E9). Current Step 4 version dated 5 February 1998.
- GCP rules of the Eurasian Economic Union (a draft).

The objective of this Statistical Analysis Plan is more detailed, compared to Section 9 of the trial protocol, description of the main principles of the protocol-based statistical analysis, description of the primary and secondary endpoints analysis methods, as well as other data obtained during the trial.

This Plan stipulates for consistence of the scheduled and conducted statistical analysis to the trial protocol, including definition of the analysis data sets, transformations and calculations for the endpoints, observations quantity needed, etc. No changes in this Statistical Analysis Plan compared to the trial protocol are envisaged.

2. Trial endpoints

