3.10 Significance level

All statistical analyses in this trial will be conducted at 95% significance level (a threshold p value for confirmation of statistical significance is below 0.05), except for the primary endpoint where a one-sided statistical criterion will be used with 95% significance level (a threshold p value is below 0.05). The two-sided statistical criteria will be used for all other parameters.

For the primary endpoint evaluation, 90% CI will be calculated for the proportions difference with further evaluation of its lower boundary limit.

4 Analysis plan

For non-inferiority confirmation, a two-sided 90% CI will be calculated for the proportion difference of the primary efficacy parameters (no pain after 3 days of therapy on Day 4 according to TSS) with further evaluation of its lower boundary limit.

A non-inferiority conclusion will be made relating to the primary parameter only which will confirm the claimed efficacy. Secondary variables (including secondary efficacy and safety parameters) will be used for the research interest. Correction for multiple comparisons is not envisaged due to the trial arms number.

Descriptive statistics will include data for all randomized patients. Descriptive statistics parameters to be calculated for the quantitative variables are listed below:

- Quantity of observations (n);
- Arithmetic mean (M);
- Standard deviation (SD);
- 95% confidence interval for the mean (95% CI);
- Minimal value (min.);
- Maximal value (max.);
- Median (Me);
- Interquartile range (IQR).

For the variables presented as qualitative and serial parameters, the absolute (n) and relative (%) incidences will be calculated for every category, as well as 95% CI (unless otherwise specified).

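### SAP 3.7 lets the sponsor stop on efficacy after an optional open-label look with no alpha correction, and nothing rules out a non-inferiority claim at that look

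*SAP*

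**What the plan says.** Protocol 9.8 provides for an optional look: "An interim analysis may be conducted by the Sponsor's decision after receipt of efficacy data" on Day 4 for at least 100 patients in each arm. The synopsis describes the same look. Neither gives a stopping rule, a boundary or an alpha level for it.

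SAP 3.7 repeats the look and adds two things. On the interim efficacy and safety results the sponsor "shall be entitled to decide to discontinue the trial prematurely". It then says: "No significance level correction for the interim statistical analysis is envisaged".

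On stopping in general, Protocol 9.4 says: "The trial may be terminated under conditions described in Section 4.6 of this protocol". Section 4.6 lists new toxicological, pharmacological or SAE data, the incidence or severity of AEs, a regulator's decision, and "other reasons including administrative ones". Efficacy is not named. SAP section 1 nevertheless states: "No changes in this Statistical Analysis Plan compared to the trial protocol are envisaged".

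The two documents also disagree on the level of the primary test. Protocol 9.3 has "a threshold p value is below 0.025", whereas in SAP 3.10 "a one-sided statistical criterion will be used with 95% significance level", with a p threshold of 0.05. Both use a two-sided 90% interval for the decision.

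**The concern.** The trial has one confirmatory conclusion, non-inferiority on the primary endpoint, and it is meant to support registration. SAP 3.7 ties a right to stop to the efficacy results, mentions alpha correction only to decline it, and says nothing about whether non-inferiority may be declared at that point. If it may, the same criterion can be met at either of two looks and the type I error exceeds the stated level.

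The setting offers little protection. The trial is open, the investigator scores the primary endpoint, and the sponsor decides both whether to look and when, since the timing is only a minimum of 100 per arm. That decision can therefore depend on results already seen. The multiplicity remark in SAP section 4 concerns the number of arms, not repeated looks.

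**Working it through.** **Inputs.** One-sided alpha is 0.025 (Protocol 9.2 and 9.3) or 0.05 (SAP 3.10). The earliest look is at 100 per arm (SAP 3.7, Protocol 9.8). The final number per arm is 128 completers or 140 randomised (Protocol 9.2). Assumed response is 65% against 63%, with a margin of 14.5 points (Protocol 9.2). The documents give no error rate for the interim and final analyses taken together, so there is no figure of theirs to reproduce first.

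**Step 1: two looks at the same critical value.** At the null boundary the interim and final test statistics are approximately bivariate normal with correlation √(n₁/n₂). The overall one-sided error is 1 − P(Z₁ < c, Z₂ < c), where c = 1.645 for 0.05 and c = 1.960 for 0.025. For 100 of 128, the correlation is √0.781 = 0.884. For 100 of 140 it is √0.714 = 0.845.

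| Look / final per arm | From 0.05 | Factor | From 0.025 | Factor |
|---|---|---|---|---|
| 100 / 140 | 0.0724 | 1.45 | 0.0375 | 1.50 |
| 100 / 128 | 0.0695 | 1.39 | 0.0359 | 1.44 |
| 110 / 128 | 0.0656 | 1.31 | 0.0338 | 1.35 |
| 126 / 140 | 0.0631 | 1.26 | 0.0324 | 1.30 |
| 120 / 128 | 0.0603 | 1.21 | 0.0308 | 1.23 |
| 125 / 128 | 0.0563 | 1.13 | 0.0286 | 1.14 |

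**Step 2: the same check with the plan's interval.** Four million trials per scenario were simulated at the null boundary, 48.5% (63% − 14.5 points) against 63%. Success was a Newcombe score-based lower limit above −0.145. That choice is an assumption, because the plan cites a paper comparing several methods without naming one.

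| Interval | Look / final | Final look alone | Either look | Ratio |
|---|---|---|---|---|
| 90% | 100 / 128 | 0.0492 | 0.0738 | 1.50 |
| 90% | 100 / 140 | 0.0487 | 0.0765 | 1.57 |
| 90% | 120 / 128 | 0.0491 | 0.0606 | 1.23 |
| 95% | 100 / 128 | 0.0283 | 0.0401 | 1.42 |
| 95% | 100 / 140 | 0.0276 | 0.0412 | 1.49 |
| 95% | 120 / 128 | 0.0281 | 0.0330 | 1.17 |

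With a control rate of 70% instead of 63%, the ratios for looks at 100 to 120 per arm run from 1.22 to 1.55.

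**Step 3: a boundary that holds the level.** A Lan-DeMets O'Brien-Fleming-type function spends 2[1 − Φ(z₁₋α/₂ / √t)] at information fraction t. For α = 0.025 and t = 0.781 this is 2[1 − Φ(2.241/0.884)] = 0.0112. The final bound then solves 1 − P(Z₁ < c₁, Z₂ < c₂) = α. A one-sided p bound corresponds to a two-sided interval of level 1 − 2p.

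| Overall α | Look / final | Interim p (interval) | Final p (interval) |
|---|---|---|---|
| 0.025 | 100 / 128 | 0.0112 (97.76%) | 0.0217 (95.66%) |
| 0.025 | 100 / 140 | 0.0080 (98.40%) | 0.0226 (95.48%) |
| 0.05 | 100 / 128 | 0.0266 (94.68%) | 0.0424 (91.52%) |
| 0.05 | 100 / 140 | 0.0204 (95.92%) | 0.0440 (91.20%) |

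**Step 4: power cost of that boundary.** The standard error is √[(0.65×0.35 + 0.63×0.37)/n], which is 0.0600 at 128 and 0.0574 at 140. The distance from the margin is 0.02 + 0.145 = 0.165. At 0.025 and 128 per arm the fixed design has power Φ(0.165/0.0600 − 1.960) = 78.5%.

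| Overall α | Final n | Fixed design | With look at 100 |
|---|---|---|---|
| 0.025 | 128 | 78.5% | 77.7% |
| 0.025 | 140 | 82.0% | 81.4% |
| 0.05 | 128 | 86.6% | 85.8% |
| 0.05 | 140 | 89.1% | 88.5% |

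**The case against.** The harm needs three things: the optional look is done, success is claimed there, and a second attempt follows if it fails. SAP 3.7 speaks only of stopping and never of concluding non-inferiority. The synopsis and Protocol 9.2 give 128 per arm as the minimum for analysis, which points away from a claim at 100. The open-ended ground in Protocol 4.6 arguably already permits such a stop, and the SAP is meant to be more detailed than Protocol section 9. If no claim can be made at the look, declining a correction is right.

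Much of this is fair but does not remove the problem. The 128 is a sample-size result and not a bar on analysis, and Protocol 11.3 lets the sponsor accept a smaller enrolment without counting it as a deviation. No sentence limits the look to safety or futility. The open-ended ground in 4.6 leaves the gap open: efficacy stopping appears only in the SAP, without a rule.

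Two qualifications stand. The factor is not bounded at 1.2 to 1.5: it falls to about 1.13 at 125 of 128 and reaches 1.57 in one simulated case. And all figures assume a single look at a fixed time. A look timed by the accumulating results is not covered by them.

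**Conclusion.** The concern holds, and the text is wrong as written. SAP 3.7 combines an efficacy-based right to stop, sponsor-controlled timing in an open trial and an explicit refusal to correct, without excluding a claim. If a claim is possible at both looks, the one-sided error rises by roughly 1.2 to 1.5 times for a look between 100 and 120 per arm. At the worst permitted timing that is up to 7.2% from 5%, or 3.75% from 2.5%, by the normal approximation, and slightly higher with the Newcombe limit (7.7% and 4.1%). The factor hardly depends on which alpha applies, so the 0.025 against 0.05 conflict is a separate defect and is not counted here. If the look is skipped, or cannot lead to a claim, there is no inflation.

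**What to change.** First settle the one-sided alpha between Protocol 9.3 and SAP 3.10, with the matching interval level. Then replace the no-correction sentence in SAP 3.7 with one of two rules.

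(a) State that non-inferiority cannot be claimed at the interim, that any efficacy-based stop is for futility under a pre-stated non-binding rule, and that the full alpha is kept for the final analysis. This costs no alpha but gives up an early claim. A futility rule loses some power. As an assumed example at 0.025, stopping at 100 per arm when current-trend conditional power is below 20% takes power from 78.5% to 76.2% (final 128) or from 82.0% to 79.2% (final 140). With a 10% threshold the loss is 1.1 to 1.4 points.

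(b) Pre-specify one look at 100 per arm with the Lan-DeMets bounds in Step 3, recomputed at the actual information fraction and applied as interval levels, since the plan decides on the interval. This costs under one point of power at either alpha.

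In both cases align SAP 3.7 with the protocol synopsis and Protocol 4.6, 9.4 and 9.8. The cost is wording in the two documents, and it should be done before any interim data are summarised by arm. At 0.025, power at 128 per arm is already below 80% before any change. At 0.05 it is not.

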3.8 Acceptable deadlines for visits and a scope of investigations

The data obtained at Visit 1 (Day 1) will be considered to be the initial data for the endpoint analysis.

3.8.1 Screening: Visit 1 (Therapy Day 1)

Visit 1 is scheduled for Day 1. At this visit, the doctor evaluates the patient's eligibility for the trial. If no non-inclusion criteria are met, the patient undergoes randomization, is given the study drug/comparator drug and a patient's diary, and is instructed on the patient's diary completion requirements.

Screening visit procedures:

- Signing of the Informed Consent Form;
- Demographic data (date of birth, sex, age);
- Measurement of weight and height;
- Anamnesis gathering;
- Records on the concomitant therapy;
- Evaluation of inclusion/non-inclusion criteria;
- Evaluation of the throat pain intensity according to VAS:
- Fill-in of TSS questionnaire by the Investigator;

- Physical examination (including oropharynx);
- Measurement of the main vital signs;
- Hematology;
- Biochemistry;
- Urine pregnancy test;
- 12-lead ECG;
- Evaluation of inclusion/non-inclusion criteria;
- Randomization:
- Training for administration and handling of the study drugs;
- Dispensing of the study drugs;
- Provision with the patient's diaries and training on the fill-in rules;
- Initiation of therapy with the study drugs;
- Evaluation of adverse events (including based on results of the throat and pharynx examination).

3.8.2 Efficacy evaluation visit (Visit 2, Day 4 since the therapy initiation)

Visit 2 is conducted on Day 4; the patient must visit the trial site in the fasted state and bring the filled-in diary and unused drug. If Group B patients (ANTI-ANGIN® FORMULA) did not meet recovery criteria (total $TSS \le 2$) at Visit 2 (Day 4), they will require continuation of the therapy, and some procedures for those patients will be transferred for the next day (Visit 3, Day 5), see below. The patients will keep their diaries and the unused drugs.

Visit 2 procedures for the both groups:

- Collection of complaints, actualization of anamnesis;
- Records on the concomitant therapy;
- Physical examination (including oropharynx);
- Measurement of the main vital signs;
- Evaluation of adverse events (including based on results of the throat and pharynx examination);
- Evaluation of exclusion criteria;
- Compliance evaluation (diary completion, administration of the study drugs).

Visit 2 procedures for patients from Group A (Angal S) and Group B (ANTI-ANGIN®FORMULA) who achieved recovery criteria (total TSS \leq 2):

- Hematology;
- Biochemistry;
- 12-lead ECG;
- Global evaluation of treatment tolerability during the trial by the physician and the patient;
- Return of the unused study drug;
- Return of the patient's diary.

3.8.3 Trial completion visit for Group B patients (Visit 3, Day 5)

This visit is for Group B patients only (ANTI-ANGIN® FORMULA) who did not achieve the recovery criteria (total $TSS \le 2$) at Visit 2 (Day 4).

Visit 3 is conducted on Day 5; the patient must visit the trial site in the fasted state and bring the filled-in diary and unused drug.

Visit 3 procedures:

- Collection of complaints, actualization of anamnesis;
- Records on the concomitant therapy;
- Physical examination (including oropharynx);
- Measurement of the main vital signs;
- Evaluation of adverse events (including based on results of the throat and pharynx examination);
- Evaluation of exclusion criteria;
- Return of the unused study drug;
- Return of the patient's diary;
- Compliance evaluation (diary completion, administration of the study drugs).
- Hematology;
- Biochemistry;
- 12-lead ECG;
- Global evaluation of treatment tolerability during the trial by the physician and the patient.

3.8.4 Visit 4 (a follow-up, Day 6/7 from the therapy initiation)

A follow-up visit shall be conducted by phone to find out about the patient's state and any AEs. A visit 2 days after

the therapy completion visit (e.g., on Day 6 or 7, depending on the arm and therapy duration).

Follow-up visit procedures (by phone):

Evaluation of adverse events (without the throat and pharynx examination). In case of adverse
events, the patient might be invited to visit the trial site.

3.8.5 Unscheduled visits

The unscheduled visits will be conducted when necessary, e.g., in case of the index disease deterioration, AEs, or the study drug (Angal S or ANTI-ANGIN® FORMULA) intolerability.

Every unscheduled visit, irrespective of its cause, must include the procedures listed below with completion of the relevant eCRF pages (Unscheduled Visit):

- Physical examination (including topical examination);
- TSS evaluation;
- Measurement of the main vital signs (blood pressure, heart rate, breathing rate, body temperature);
- 12-lead ECG (if it has not been done for the last 12 hours);
- Evaluation of adverse events;
- Evaluation of the concomitant therapy.

Other diagnostic and treatment procedures may be conducted depending on clinical situation and upon the Investigator's decision.

Taking into account frequency of visits, unscheduled visits may be conducted on the same days as scheduled ones but in a different time (e.g., in case of worsening the patient may visit the center in afternoon). All procedures for the scheduled visits are identical for the both arms at every trial stage, except for the Group B patients who, if the recovery criteria (total $TSS \le 2$) are not met at Visit 2 (Day 4), should continue the trial therapy and visit the trial site for scheduled Visit 3 Day 5).

3.8.6 Visit of premature discontinuation of the trial

Visit 2 procedures will be applied for the visit of premature discontinuation.

3.9 Null and alternative trial hypotheses

Based on the trial objectives, the following hypotheses were drawn for testing:

Null hypothesis (H0): Difference in the primary endpoint achievement incidence while using Angal S, the study drug, and ANTI-ANGIN®FORMULA, the original drug, for treatment of acute infectious and inflammatory pharyngeal diseases will exceed 14.5% in favor of ANTI-ANGIN® FORMULA:

$$H_0: p_1 - p_2 \le -0.145$$

Alternative hypothesis (Ha): Difference in the primary endpoint achievement incidence while using Angal S, the study drug, and ANTI-ANGIN® FORMULA, the original drug, for treatment of acute infectious and inflammatory pharyngeal diseases will not exceed 14.5% in favor of ANTI-ANGIN® FORMULA:

$$H_A: P_1 - P_2 > -0.145$$

Where p1 and p2 is the primary endpoint achievement incidence while using Angal S, the study drug, and ANTI-ANGIN® FORMULA, the original drug, respectively.

3.10 Significance level

All statistical analyses in this trial will be conducted at 95% significance level (a threshold p value for confirmation of statistical significance is below 0.05), except for the primary endpoint where a one-sided statistical criterion will be used with 95% significance level (a threshold p value is below 0.05). The two-sided statistical criteria will be used for all other parameters.

For the primary endpoint evaluation, 90% CI will be calculated for the proportions difference with further evaluation of its lower boundary limit.

4 Analysis plan

For non-inferiority confirmation, a two-sided 90% CI will be calculated for the proportion difference of the primary efficacy parameters (no pain after 3 days of therapy on Day 4 according to TSS) with further evaluation of its lower boundary limit.

A non-inferiority conclusion will be made relating to the primary parameter only which will confirm the claimed efficacy. Secondary variables (including secondary efficacy and safety parameters) will be used for the research interest. Correction for multiple comparisons is not envisaged due to the trial arms number.

Descriptive statistics will include data for all randomized patients. Descriptive statistics parameters to be calculated for the quantitative variables are listed below:

- Quantity of observations (n);
- Arithmetic mean (M);
- Standard deviation (SD);
- 95% confidence interval for the mean (95% CI);
- Minimal value (min.);
- Maximal value (max.);
- Median (Me);
- Interquartile range (IQR).

For the variables presented as qualitative and serial parameters, the absolute (n) and relative (%) incidences will be calculated for every category, as well as 95% CI (unless otherwise specified).

